Title: Probiotics and antibiotic associated diarrhea in pediatric complicated appendicitis: Prospective Controlled-Comparison Trial

NCT NCT04529980

December 15, 2020

The University of Texas Southwestern Medical Center at Dallas Institutional Review Board

Protocol Template (for Investigator Initiated Studies)

Title: Probiotics and antibiotic associated diarrhea in pediatric complicated appendicitis: Prospective Controlled-Comparison Trial

Principal Investigators:

[name], DNP, APRN, PCNS-BC [name], MSN, RN, CPN

Faculty Sponsor: [name]

Purpose: To determine the effectiveness of the use of probiotics in patients with a diagnosis of complicated appendicitis on antibiotic associated diarrhea (AAD).

Background:

Appendicitis is the most common urgent surgical procedure performed on children. Approximately one third of the population end up having complicated appendicitis with evidence of peritoneal contamination and infection or abscess requiring the use of IV antibiotics and prolonged hospital stay. Antibiotic Associated Diarrhea (AAD) is a common complication seen in both outpatient and inpatient settings in approximately a third of all patients treated with antibiotics (Mantegazza, et al., 2018). In particular, pediatric patients experience ADD 11-62% of the time and can up upwards to 80% in hospitalized toddlers (Mantegazza, et al., 2018). Current literature defines AAD as three or more liquid stools per day. The causes of AAD are often related to the use of multiple antibiotics, prolonged hospital stay and gastrointestinal surgery. Antibiotics often disturb the normal enteric microbiome in the gut and allow for an increased growth of pathogens (Hojsak, 2017). AAD can occur as late as six to eight weeks after antibiotic exposure.

Probiotics are defined as live microbial organisms that when administered in sufficient amounts, can provide a protective benefit to the host (Hojsak, 2017). Use of probiotics in a pediatric population exposed to antibiotics and gastrointestinal surgery such as an appendectomy may provide a protective effect and prevent ADD (Alper, Zangwill, LaRue & Manheimer, 2017; Hayes & Vargas, 2016). In a meta-analysis of randomized controlled trials in pediatrics, literature found that treatment with *Lactobacillus rhamnosus GG* (LGG) reduced in risk of ADD from 23% to 9.6% (RR, 0.48; 95% Cl, 0.26 to 0.89) (Szajewska & Kolodziej, 2015). Studies indicate it is suggested to administer LGG simultaneously with the initiation of antibiotic therapy, before the modification of gut microbiota and overgrowth of pathogens (Szajewska & Kolodziej, 2015).

Lactobacillus rhanmosus GG(LGG®)(Culturelle) is an over the counter dietary supplement that can help to restore the balance in the gut by promoting colonization to support better digestion and immune health. As such, this dietary supplement is not reviewed and approved by the FDA. This study does not intend to investigate route of administration, dose, patient population, or other factor that significantly increases the risk (or decreases the acceptability of the risk) associated with the use of the dietary supplement.

At Children's Medical Center, we see over 1000 cases of appendicitis a year with approximately 1/3 of those patients being complicated appendicitis. Our current treatment at Children's Medical Center for

complicated appendicitis follows two pathways: 1) drainage and deferred appendectomy approximately 6 to 8 weeks later or 2) immediate appendectomy. All children are typically admitted to the hospital for 3 to 5 days, receive a course of IV antibiotics while in hospital and are discharged with oral antibiotics to complete their treatment. There has been an increase in the number of patients receiving prescribed probiotics after surgery.

We propose to perform a randomized controlled trial where one group of patients receive probiotic therapy and another group of patients does not.

We hypothesize patients given probiotics after a diagnosis of complicated appendicitis with immediate appendectomy who receive antibiotic treatment during their inpatient stay will decrease the overall length of stay (LOS) by 25% vs the LOS in those patients who do not receive probiotics.

3. Concise Summary of Project:

Upon IRB approval, patients admitted to the pediatric surgery service with complicated appendicitis who undergo an immediate appendectomy will be approached about participation in the study. Once written consent has been obtained, patients will be randomized into one of two potential study groups. Those randomized to the treatment group will be given probiotic therapy until discharge, while those randomized to the placebo group will be given a placebo until discharge. Data will be collected from the Electronic Health Record (EHR) at Children's Medical Center will include MRN, standard demographics, length of stay, presence or absence of diarrhea, ambulation/activity level, abdominal pain, stool counts, surgical history, medications, emergency department visits and readmission rates. Data will be stored in a CMC/UTSW secured RedCap with access only granted to study team members.

4. Study Procedures:

Design. Prospective Randomized Controlled Trial

Sample.

Data will be obtained from the electronic health record (EHR) from a convenience sample of patients in a single-center pediatric inpatient surgery unit with a diagnosis of complicated appendicitis that undergoes an immediate appendectomy.

Patients will be randomized into two study groups using randomization and utilizing a sealed envelope randomization plan. 120 envelopes will be sealed with a standard sized document marked "probiotic treatment" and 120 envelopes will be sealed with a standard sized document marked "placebo". 240 envelopes will be thoroughly shuffled then labeled sequentially from 1-240 in pen. Envelopes will be placed in a plastic container in numerical order ready for use. One group of 120 patients will be given probiotic therapy until discharge and the other group of 120 patients will be given a placebo until discharge

Methods:

After the appendectomy, patients who meet the inclusion criteria and none of the exclusion criteria will be approached by the study team and offered participation for this study. Patients and families will be approached after their surgery on the inpatient floor. A member of the research team will provide families information about the study in their preferred language (English/Spanish). Aconsent will be signed and scanned into to the patient's medical record.

Those who are in agreeance will be consented for the study following all IRB procedures. Randomization will be used to allocate patients into treatment and control group. The treatment group includes 120 patients who have immediate appendectomy and will receive probiotics. The control group includes 120 patients who have an immediate appendectomy and will receive a placebo. Patients in the treatment group will receive a standard dose of Lactobacillus rhamnosus GG capsule twice a day until discharge. The control group will receive a placebo until discharge. If the patient is unable to swallow the probiotic capsule or placebo, the capsule can be opened and sprinkled with food. Current antibiotic standard of care for complicated appendicitis patients includes: ceftriaxone RTA 50mg/kg dose every 24 hours x 7 days and metronidazole RTA 30mg/kg dose every 24 hours x7 days. In patients with a sensitivity to ceftriaxone, metronidazole RTA 30mg/kg dose every 24 hours x7 days and ciprofloxacin 10-15 mg/kg every 8 hours x 7 days will be administered.

Treating medical team and patients/family will be blinded to whether patient is on probiotic or placebo.

[figure not shown]
Data will be collected as stated in section titled, "Concise Summary of Project."

5. Criteria for Inclusion of Subjects:

- Patients with a post-operative diagnosis of complicated appendicitis who undergo an immediate appendectomy.
- Patients between the ages of 4 and 18 years of age.

6. Criteria for Exclusion of Subjects:

- Patients diagnosed with a complicated appendicitis with deferred appendectomy or nonperforated appendicitis
- Patients that have a history of being immunosuppressed, on immunosuppression therapy, or long-term steroid therapy within the last month.
- Patients that have central line access.
- Patients under 4 years of age.
- Patients that are developmentally delayed and cannot ambulate at baseline. •
- Patients with significant past medical history.
- Patients that are in Child Protective Services custody. •
- Patients that are incarcerated.
- Patients that are pregnant. •
- Patients that speak languages other than English and Spanish.

Study Procedures

7. Sources of Research Material:

All participants will be patients under the care of the General Surgery Department. Information from the Children's Medical Center EHR will be reviewed. Data on outcomes such as length of stay, presence or absence of diarrhea, ambulation/activity level, abdominal pain, surgical history, medications, emergency department visits, readmission rates and stool counts will be extracted from medical records. Standard demographic data will also be obtained.

8. Recruitment Methods and Consenting Process:

After confirmed complicated appendicitis diagnosis, patients and families will be approached by the study team to participate in the study. If families agree to participate, written consent will be obtained, and the patient will be randomized to a study group.

9. Potential Risks:

Inadvertent disclosure of personal medical information. Special precautions are mentioned below in the paragraph *Procedures to Maintain Confidentiality*.

There are potential risks for patients taking probiotics. There have been reported accounts of sepsis in immunosuppressed patients receiving probiotics. Our study will exclude patients with a history of being immunosuppressed, on immunosuppression therapy, or long-term steroid therapy within the last month.

There is a potential risk of psychological stress. Some of the questions we will ask may make the patient/legal guardians feel uncomfortable.

10. Subject Safety and Data Monitoring:

All data will be stored on a password protected computer approved by UTSW and CMC. Access to study data will be restricted to authorized study personnel only.

All data will be stored on a password protected computer in a RedCap system approved by UTSW and CMC. Access to study data will be restricted to authorized study personnel only.

The Principal Investigators and faculty sponsor will review all patient outcomes on a monthly basis. All adverse events, expected and unexpected will be reviewed within 24 hours by the study team and reported to the DSMB and the IRB as per policy.

11. Procedures to Maintain Confidentiality:

All patient information and case report forms will be kept in a locked office with limited access. All computer files will be password protected, encrypted and stored on a secure server. Access will be limited to study team members only. Data will be collected and stored in a secured CMC server in RedCap. The case report includes a unique subject number. The data will be collected, analyzed, and archived following strict confidentiality guidelines. The Investigator will consider all information, results, discoveries, records accumulated, records acquired, or deductions in the course of the study as confidential; other than that information to be disclosed by law.

12. Potential Benefits:

There may be benefit to those patients who receive a probiotic during their course of treatment in a reduction of the incidence of AAD. Future patients may benefit if the protocol proven to be effective in decreasing the incidence of AAD.

13. Sample size calculation

Based on the patient population in Children's Medical Center Dallas, the mean and standard deviation of LOS is 114 and 75.6 hours, respectively. The LOS in the probiotic group is expected to be 75% of the control group. With 120 patients in each group, we have 83% of power to detect statistically significant difference in LOS between the probiotic group and control group.

14. Biostatistics

Descriptive analyses of the continuous and categorical data were performed using means, confidence intervals, proportions and frequencies. Wilcoxon Rank Sum test will be used to compare the LOS, as well as the number of diarrheas, between the treatment group and control group. To investigate which type of patients benefits the most from the treatment, regression analysis will be used to model log-transformed LOS. The independent variable will be treatment type and prognostic factors. The statistical analyses were performed with SAS 9.4.

References:

- Alper, B. S., Zangwill, M., LaRue, J., & Manheimer, E. W. (2017). Point of care application of: 'Probiotics for the prevention of pediatric antibiotic-associated diarrhea' (Cochrane review). *European Journal of Integrative Medicine, 12*: 129-130. https://doi.org/10.1016/j.eujim.2017.06.001

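### The Purpose is antibiotic-associated diarrhea (AAD), but hypothesis and power rest on length of stay, and the one between-arm diarrhea test is on a count with no stated unit or window

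*Combined protocol and SAP*

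**What the plan says.** The title, the Purpose and Section 12 (Potential Benefits) are about AAD. The Purpose reads "To determine the effectiveness of the use of probiotics in patients with a diagnosis of complicated appendicitis on antibiotic associated diarrhea (AAD".

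The only hypothesis, at the end of the Background, is that probiotics "will decrease the overall length of stay (LOS) by 25% vs the LOS in those patients who do not receive probiotics". Section 13 gives power for that outcome alone: "we have 83% of power to detect statistically significant difference in LOS". No endpoint is called primary or secondary.

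Section 3 lists among the data to be collected "length of stay, presence or absence of diarrhea, ambulation/activity level, abdominal pain, stool counts", and Section 7 repeats these items. Both sections also list emergency department visits and readmissions. Each arm "will be given probiotic therapy until discharge, while those randomized to the placebo group will be given a placebo until discharge".

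Section 14 names one between-arm test for diarrhea: "Wilcoxon Rank Sum test will be used to compare the LOS, as well as the number of diarrheas". Its regression models log LOS. Its descriptive sentence, "Descriptive analyses of the continuous and categorical data were performed using means, confidence intervals, proportions and frequencies", names no variable and no contrast between arms.

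The Background reports a definition of AAD (at least three liquid stools in a day) as what the literature uses; the trial does not adopt it as an endpoint. The Background also cites a meta-analysis in which the probiotic "reduced in risk of ADD from 23% to 9.6% (RR, 0.48; 95% Cl, 0.26 to 0.89". One figure in Section 4 was not available for this review, so statements here about what is absent apply to the readable text.

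**The concern.** There are two linked problems.

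First, the question the trial sets itself and the question it is designed to answer differ. Without a named incidence contrast, an adopted definition, a window or a primary endpoint, an AAD result could be built in several ways after the data are seen: stools, episodes, days with diarrhea, or children affected.

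Second, the one planned diarrhea comparison may be tied to LOS. The natural reading of the count is a total over the inpatient stay, because study product stops at discharge and no stool collection after discharge is described. This is an inference. On that reading, children who go home sooner have less time in which events can be counted. The trial expects LOS to fall by 25%, so a lower count in the probiotic arm could reflect shorter stays rather than less diarrhea per day, and could be reported as AAD prevention.

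**Working it through.** **1. The plan's own power figure.** Inputs from Section 13: mean LOS 114 h, SD 75.6 h, ratio 0.75, 120 per arm. Two-sided alpha of 0.05 is assumed, as none is stated.
- Difference: 114 × 0.25 = 28.5 h.
- Standard error: 75.6 × √(2/120) = 9.76 h.
- Power: Φ(28.5/9.76 − 1.96) = Φ(0.96) = 83.2%; with the t distribution, 82.9%.

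The stated 83% is reproduced from LOS inputs alone. No AAD rate enters the sample size.

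**2. What 120 per arm gives for AAD incidence.** Power = Φ{[|p₁ − p₂|√n − 1.96√(2p̄(1 − p̄))] / √[p₁(1 − p₁) + p₂(1 − p₂)]}, with p̄ the mean of p₁ and p₂. The cited 23% and 9.6% give a crude ratio of 9.6/23 = 0.42, not the quoted 0.48, so both were run.

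| Control | Probiotic | Power |
|---|---|---|
| 23% | 9.6% | 81% |
| 23% | 23 × 0.48 = 11.04% | 70% |
| 11% | 11 × 0.48 = 5.28% | 37% |
| 62% | 62 × 0.48 = 29.76% | 99.9% |

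For the first row: (0.134 × 10.954 − 1.96 × 0.5224)/0.5137 = 0.864, and Φ(0.864) = 80.6%. The 11% and 62% are the ends of the pediatric range in the Background. The documents do not show that any of these are in-hospital rates.

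**3. Dependence of a per-stay count on LOS.** With the same daily rate r in both arms and diarrhea continuing through the stay, the ratio of expected counts is (r × 85.5)/(r × 114) = 0.75 with no effect on diarrhea. In simulations (lognormal LOS, LOS × 0.75 in the probiotic arm, 0.25 to 2 events a day, gamma shape from 0.25 to plain Poisson), the Wilcoxon test on the count was significant in:
- 11–85% of trials if diarrhea runs through the stay;
- 6–29% if it is confined to the first 3 days;
- 4–10% if it is confined to the first 2 days;
- 4–6% when LOS does not differ either.

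**4. Dependence of in-hospital incidence on LOS.** Assume lognormal LOS with σ² = ln(1 + (75.6/114)²) = 0.364, so σ = 0.604 and μ = ln 114 − 0.182 = 4.554. Assume a constant hazard h, so incidence = E[1 − exp(−h·LOS)]. Choose h to give 23% in controls, keep it for the probiotic arm and multiply LOS by 0.75: incidence becomes 18.0%, and 18.0/23 = 0.78. A hand check with every control child staying the same time gives 1 − 0.77^0.75 = 17.8%. In a common early window the ratio is closer to 1: 0.96 at 48 h and about 0.92 at 72 h.

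**5. Agreement in direction is not a safeguard.** Under the no-effect model of step 4, in-hospital incidence shows a significant benefit in 16% of trials. Among those, the early window points the same way in about 90% (48 h) or 98% (72 h), because it is nested in the stay.

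**6. Time origin.** Steps 3 to 5 treat the whole LOS as time observed. Sections 3 and 4 place consent and randomisation after surgery. With an assumed lag of 12–24 h, leaving within 48 h of randomisation means a total stay under 60–72 h.
- Control: Φ((ln 60 − 4.554)/0.604) = 22%, and with ln 72, 32%.
- Probiotic (μ = 4.554 + ln 0.75 = 4.266): 39% and 51%.
- With no lag: 13% and 26%.

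**The case against.** **Diarrhea is already compared between arms.** This stands. The Purpose speaks of effectiveness on AAD, not of incidence, and a count is a permissible measure. A reader might infer that the plan commits to no between-arm contrast for its Purpose; the Wilcoxon test in Section 14 shows otherwise. What remains is narrower: the count is undefined, and no contrast of incidence is named.

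**Proportions and confidence intervals will be reported.** True, and a crude difference could be derived from them by arm. The sentence is descriptive, though, and names neither AAD nor a comparison.

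**LOS is plainly the intended primary endpoint.** The hypothesis and Section 13 imply it. That is a reason to say so and to word the Purpose and conclusions accordingly.

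**The modelled figures rest on a scenario the documents do not describe.** This also stands. LOS falling with no effect on diarrhea is assumed. The lognormal model places only 33% of control children at 72–120 h, although the Background says stays are typically 3 to 5 days. The calculations also start the clock at admission. They show direction and plausibility only.

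Two other stronger readings fail. A reader might infer that 83% is wrong or that 240 children are too few for AAD. The figure reproduces, and AAD power runs from 37% to 99.9% over the cited rates. A reader might also infer that the count test has an inflated false-positive rate. It does not: when neither LOS nor daily rate differs it rejects in 4–6% of trials. A lower count from a shorter stay is a real difference between arms; the risk lies in how it is interpreted.

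**Conclusion.** The point holds and is worth fixing, though the trial remains analysable as planned. The mismatch between Purpose and design, the missing incidence contrast and the undefined count can be read directly from the text, subject to the one unseen figure; confidence in these is high and needs no model.

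The dependence on LOS is conditional on the count, or the incidence, being taken over the inpatient stay. Its direction is clear. Its size cannot be fixed from the documents. The fall from 23% to 18.0% rests on a constant hazard, lognormal LOS, a 25% shorter stay, no AAD effect and the whole stay counted as observed, and should be quoted only as an illustration.

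**What to change.** In Section 14, with matching wording in the Purpose and Section 13:

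1. Add a between-arm comparison of the proportion of children with in-hospital AAD, with risk difference, risk ratio and 95% CI. Use the Background definition where records allow, otherwise the recorded yes/no for diarrhea.
2. State the unit of the diarrhea count (stools, episodes or days) and its window, counted from randomisation.
3. Report beside it one analysis that accounts for time observed from randomisation. Base any claim of AAD prevention separate from shorter stay on that analysis's own estimate and 95% CI, not on agreement in direction. If records are dated, use incidence in a fixed early window common to both arms, its length set before unblinding. If not, use a count model with inpatient days after randomisation as offset, stating that it assumes diarrhea is spread over the stay. If neither is possible, state the LOS dependence as a limit on the AAD conclusion.
4. Label one endpoint primary before unblinding. LOS may stay primary if the Purpose and conclusions match and AAD incidence is the named key secondary. Any AAD power given in Section 13 should be a range.

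The cost is wording and a little analysis, with the same 240 children and the data already listed. The documents do not say that stools are dated, hence the fallbacks.

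There are downsides. AAD power may be well below 83%. The fixed window has less power still: 40–51% at 48 h and 52–68% at 72 h for in-hospital rates of 23% against 9.6% or 11.04%. Those figures count the whole stay as observed, so they are probably optimistic given the early departures in step 6. The offset model can err the other way: with diarrhea confined to the first 2 days and no AAD effect, it shows a rate ratio of about 1.27 against the shorter-stay arm. In-hospital AAD also misses later cases, which the Background says can arise up to 6–8 weeks after exposure; the emergency department and readmission data may catch some.

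### The diarrhea outcome has no defined window, and if counts are effectively in-hospital the unadjusted comparison will favor whichever arm goes home sooner

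*Combined protocol and SAP*

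**What the plan says.** The title and Purpose concern the effect of probiotics on AAD, with no time limit. The Background gives a definition from the literature, "Current literature defines AAD as three or more liquid stools per day", but no section adopts it as an outcome rule. The Background also states that "AAD can occur as late as six to eight weeks after antibiotic exposure". Children typically stay 3 to 5 days and "are discharged with oral antibiotics to complete their treatment".

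Sections 3 and 7 draw presence of diarrhea, stool counts, emergency department visits and readmissions from the site's electronic health record. No assessment window is given for any of them, and no visit, call, diary or survey after discharge is described. Study product is given until discharge (sections 3 and 4).

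The hypothesis is that probiotics "will decrease the overall length of stay (LOS) by 25% vs the LOS in those patients who do not receive probiotics". Section 13 bases the sample size on length of stay (LOS). Section 14 compares LOS and the count of diarrheas by the Wilcoxon rank sum test, with no allowance for time observed. Section 12 adds: "Future patients may benefit if the protocol proven to be effective in decreasing the incidence of AAD".

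**The concern.** Two features of the plan combine badly.

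- **No route for later cases.** A child who develops liquid stools at home and does not return to this hospital has no specified way into the dataset. The antibiotic course continues at home, and the protocol itself says onset can be late.
- **Unequal observation time.** To the extent that counts stop at discharge, each child's observation time is that child's stay, which is the quantity the trial expects the probiotic to shorten. A raw count then mixes how often diarrhea occurs with how long anyone was recording it.

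The second feature could mislead even if no case started late. A trial that succeeded on LOS could report fewer diarrheas on probiotic and read this as AAD prevention, although the daily rate was the same in both arms.

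**Working it through.** **Inputs from section 13:** control LOS mean 114 h, SD 75.6 h; probiotic LOS 75% of control; 120 per arm. Alpha is not stated; two-sided 0.05 is assumed.

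**1. The plan's own figure.** Difference = 0.25 × 114 = 28.5 h. Standard error = 75.6 × √(2/120) = 9.76 h. Power = Φ(28.5/9.76 − 1.96) = Φ(0.96) = 83%. The stated 83% reproduces. It concerns LOS only and does not bear on diarrhea.

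**2. Time observed, if counts are in-hospital.** Control: 114/24 = 4.75 days. Probiotic: 0.75 × 4.75 = 3.56 days.

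**3. Expected counts with no effect on diarrhea.** For a common daily rate r, the ratio of expected counts is (r × 3.56)/(r × 4.75) = 0.75, whatever r is.

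**4. The same effect on a yes/no outcome.** Take the 23% risk quoted in the Background as an illustrative in-hospital control incidence. Daily hazard = −ln(1 − 0.23)/4.75 = 0.055. Over 3.56 days, incidence = 1 − exp(−0.055 × 3.56) = 17.8%, a ratio of 0.77 with no true effect. With 120 per arm, a two-sided test of 23% against 17.8% rejects about 17% of the time.

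**5. Rejection rate of the planned Wilcoxon test.** Simulation with 120 per arm, log-normal LOS with means 114 and 85.5 h, coefficient of variation 75.6/114 = 0.66, and equal daily rates in both arms. The rates and their spread between children are assumptions, because the documents give neither.

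| Assumed diarrhea pattern | Rejection |
|---|---|
| Equal LOS in both arms (reference) | about 5% |
| Low rate, 0.055 per day | about 10% to 16% |
| 0.25 to 2 per day, strong overdispersion (gamma shape 0.3) | 12% to 14% |
| 0.25 to 2 per day, moderate overdispersion (gamma shape 1) | roughly a quarter to a third |
| 2 per day, one Poisson rate shared by every child | about 84% |
| 3 per day in only 23%, 33%, 62% or 80% of children, none in the rest | 6%, 8%, 23%, 54% |

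**6. Candidate remedies under the same equal-rate conditions.** A rate analysis with observed time as offset rejects in about 4% to 8%. A Wilcoxon test on each child's per-day rate still rejects in about 9% to 11% when counts are low, so it is only a partial remedy.

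**7. Calendar coverage.** A mean stay of 4.75 days is 4.75/56 = 8.5% to 4.75/42 = 11.3% of a six-to-eight-week period. Against the 7-day courses in section 4, a 3 to 5 day stay covers 3/7 = 43% to 5/7 = 71%. These are shares of time, not of cases.

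**The case against.** A reader might infer that diarrhea is captured only up to discharge and that the trial therefore cannot support its conclusion on AAD incidence. The documents do not go that far.

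- **No cut-off is stated.** The discharge limit governs study product. Emergency department visits and readmissions, normally post-discharge events, are in the same extraction and could catch some later cases that return to this hospital. In-hospital capture is a likely reading, not a stated rule. The undefined window is the fault.
- **No conclusion on incidence is stated.** AAD is the purpose and a conditional benefit. The hypothesis and powered endpoint are LOS.
- **Late onset is given only as an outer limit.** No share of cases starting after discharge appears, so 8% to 11% of calendar time says nothing about the proportion missed.
- **The high rejection figures depend on strong assumptions.** About 84% needs every child to share one high rate. If the count means episodes, or most children have none, the inflation is much smaller. If the probiotic changes neither LOS nor diarrhea, the test keeps its 5% level.
- **An in-hospital comparison is legitimate.** Product stops at discharge, and a randomized, blinded comparison of diarrhea before discharge remains possible if it is labeled as such.

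All of this stands. It does not answer the unequal observation time: section 14 makes no allowance for it, and the hypothesis predicts it. The Wilcoxon test validly compares total in-hospital counts, but a difference there would not show a lower tendency to AAD.

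**Conclusion.** The concern holds in a limited form. The plan defines neither the diarrhea outcome nor its window and has no active ascertainment after discharge, so an AAD finding would in practice describe mainly the hospital stay. If counts are effectively in-hospital, the planned comparison is biased toward the arm with the shorter stay. Under the trial's own LOS hypothesis, and with no effect on the daily rate, the expected count is 25% lower on probiotic.

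The direction is firm; the effect on the test is not. About 10% to 84% rejection instead of 5% is an illustration, and it falls to 6% to 8% if diarrhea is confined to a quarter to a third of children. These figures assume a constant daily rate, log-normal LOS, two-sided 0.05, no dropout, and the whole stay as observation time. Approach and consent follow surgery, so time from randomization is shorter in both arms. If the full 28.5 h difference falls after randomization, the relative gap exceeds 25%.

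The LOS comparison and its 83% power are not affected.

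**What to change.** 1. In sections 3 and 14, define the diarrhea outcome: what is counted (stools, days or episodes), by what rule, and over what window.
2. Unless post-discharge collection is added, restate the Purpose and section 12 as diarrhea before discharge.
3. In section 14, replace the unadjusted count comparison with a rate analysis using observed hospital days as offset, for example negative binomial regression, or Poisson regression with robust standard errors, with log LOS as offset. Where the record allows, count events and days from randomization. Alternatively, compare over a common window from randomization, short enough that nearly all children are still in hospital.
4. State a window for emergency department visits and readmissions.

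**Cost:** wording and a modest amount of modeling, with no new procedure. The conclusion becomes narrower. The rate analysis assumes that discharge timing is not itself driven by diarrhea; if children with diarrhea are kept longer, the rate is distorted too, and the common window is the safer check.

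**Optional:** a family survey after discharge would allow a fixed window such as 8 weeks and a broader AAD claim. It is an added procedure, with non-response and recall error. Section 9 warns that "Some of the questions we will ask may make the patient/legal guardians feel uncomfortable", but no questionnaire is described, so this sentence cannot be taken as a survey already planned.
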